4.8.1.1 Subsets

- Separate summary tables by SOC and PT will be presented for treatment-emergent SAEs.
- Separate summary tables by SOC and PT and by SOC, PT and maximum severity will be presented for related TEAEs.
- Separate summary tables by SOC and PT will be presented for treatment-emergent related SAEs.

CONFIDENTIAL

Sponsor:	Zambon S.p.A.	Protocol Number:	Z7224L01
----------	---------------	------------------	----------

- Separate summary tables by SOC and PT will be presented for treatment-emergent AEs leading to the permanent discontinuation of IMP. An AE leading to discontinuation is an AE with action taken with IMP equal to "Permanently discontinued".
- Separate summary tables by SOC and PT will be presented for treatment-emergent fatal SAEs.
- Treatment-emergent SAEs and fatal AEs will be listed separately.
- The most frequent MedDRA PTs ($\geq 5\%$ of subjects with events in any treatment group) will be presented overall and by treatment. PTs will be used for tabulation, sorted by decreasing overall frequency.

All other information collected will be listed, as appropriate. Additionally, listings will display relative day of AE onset.

The relative day of AE onset will be calculated as follows:

- For pre-treatment AEs:
 - AE onset date - date of first IMP dose (if AE onset date is completely known);
 - missing (if AE onset date is incomplete or unknown).
- For TEAEs:
 - AE onset date - date of first IMP dose +1 (if AE onset date is completely known);
 - missing (if AE onset date is incomplete or unknown).

Notes:

- AEs will be coded using MedDRA version 19.1 or higher (please refer to the final Data Management Plan for the latest coding information).
- Terms will be displayed in descending overall frequency (and then alphabetically) of SOC and in descending overall frequency (and then alphabetically) of PTs within each SOC.

4.8.2 Spirometry Results

The following spirometry parameters will be summarised for each visit, as applicable, by treatment group and overall:

- FEV₁ (L);
- Predicted FEV₁ (%);
- FVC (L);
- Predicted FVC (%);
- Change in FEV₁ (L) from pre-salbutamol/albuterol intake to 30 minutes post-IMP.

Absolute value and change from baseline at each visit will be described by means of summary statistics for continuous variables.

CONFIDENTIAL

Sponsor:	Zambon S.p.A.	Protocol Number:	Z7224L01
----------	---------------	------------------	----------

The number and percentages (along with exact 95% CIs) of subjects experiencing bronchospasm at Visit 7 (End of Treatment) following IMP administration as clinically (as collected in the Spirometry eCRF forms) or spirometrically (>15% decrease in FEV₁ from pre-salbutamol/albuterol intake to 30 minutes post-IMP) determined will be summarised by treatment. The number of subjects experiencing bronchospasm at all other visits will be listed. The subject will be considered spirometrically to have had a bronchospasm if presenting >15% decrease in FEV₁ from pre-salbutamol/albuterol intake to 30 minutes post-IMP or a positive answer to the above question.

The relative risk for colistimethate sodium/placebo will be provided with 95% asymptotic CIs. Treatment differences will be assessed using a Fisher Exact test. Subjects with no available result will be excluded from the analysis.

Notes:

- Change in FEV₁ (L) will be calculated as FEV₁ 30 minutes post-IMP – FEV₁ pre-salbutamol/albuterol intake;
- Percentage change in FEV₁ (%) will be calculated as 100*(change in FEV₁ [L] / FEV₁ pre-salbutamol/albuterol intake).

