 18. significant abnormality in clinical evaluations and/or laboratory tests (physical examination, vital signs, haematology, clinical chemistry, clinically relevant impaired renal function, defined as serum creatinine levels ≥ 2.0 x upper limit of normal, ECG) endangering the safe participation of the patient in the study at the Screening Visit (Visit 1) and during the study;
 19. participated in another investigational, interventional trial within 30 days prior to the Screening Visit (Visit 1);
 20. in the opinion of the Investigator not suitable for inclusion for whatever reason.
-

Outcome measures:

Primary Efficacy Variable:

Mean annual pulmonary exacerbation rate.

Secondary Efficacy Variables:

- CCI [REDACTED]
- [REDACTED]
- [REDACTED]
- [REDACTED]
- [REDACTED]
- [REDACTED]
- [REDACTED]
- [REDACTED]

Safety Variables:

- incidence of treatment emergent adverse events (TEAEs);
 - absolute changes in percent-predicted FEV₁ from baseline to each post-baseline visit;
 - number of subjects experiencing bronchospasm clinically or spirometrically determined following IMP administration;
 - CCI [REDACTED] as determined by *in-vitro* CCI [REDACTED] from Screening/Randomisation (Visit 1/Visit 2) to Visits 3, 5 and end of treatment (Visit 7) as well as on CCI [REDACTED] from Exacerbation Visits and clinic visits due to pneumonia;
-

-
- from Screening (Visit 1) to End of Treatment (Visit 7);
 - haematology, clinical chemistry and renal function tests;
 - physical examination and vital signs data;
 - 12-lead electrocardiogram.

Statistical Analysis

Primary analyses will be performed on the modified intention-to-treat (mITT) population with exclusions from the ITT defined and justified in the Statistical Analysis Plan (SAP). A supportive analysis will be conducted using a per-protocol (PP) population excluding subjects with major protocol deviations.

Annual pulmonary exacerbation rates will be compared between treatment groups using a Poisson regression model allowing for over-dispersion and also considering pooled site, use of stable concomitant therapy with oral macrolides and pulmonary exacerbation frequency in the 12 months preceding Visit 2 as covariates.

The primary analyses detailed above will be a comparison of colistimethate sodium against placebo at the end of the 12-month, double-blind phase. Full details will be provided in the SAP.

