8.2. VISIT 2 - RANDOMISATION VISIT (DAY 0)

At Visit 2 (Randomisation), the following procedures will be performed:

- check if subject is still eligible according to inclusion and exclusion criteria and check of screen failure criteria for Visit 2;
- documentation of concomitant medications (including azithromycin/erythromycin/clarithromycin use) or treatments;
- record details of any AEs since the Screening Visit (Visit 1);
- training and completion of CCI [REDACTED] on electronic clinical outcome assessment (eCOA) device before other study procedures;
- dip-stick pregnancy test for women of child-bearing potential.
- collection of CCI [REDACTED];
- randomisation by Interactive Web Response System (IWRS) and treatment kits assignment;
- dispensing of, and subject training on, CCI [REDACTED] device including the use of the [REDACTED] disc;
- subject training on IMP preparation, inhaled bronchodilator use and subject's card dispensing;
- first IMP administration under clinical supervision (at least 10 minutes after inhalation of short-acting bronchodilator; if the patient prefers not to use a bronchodilator this should be documented and the lack of bronchial hyper-reactivity after IMP administration documented);
- spirometry, including assessment of FEV₁ and FVC pre-bronchodilator and 30 ± 10 minutes post-IMP dose (**Note:** in case of a >15% decrease - not due to poor technique - in FEV₁ from pre-bronchodilator baseline after first IMP intake, or clinically determined bronchospasm, the subject will be immediately withdrawn from the trial);
- dispensing of sufficient IMP kits and inhaled bronchodilator for the treatment period until Visit 3;
- instruction of subjects on actions to be taken in case of CCI [REDACTED].

The Investigator will arrange an appointment for Visit 3 (28 days ± 1 week).

In addition, the Investigator will call the subject after 1 week to ensure that there are no problems with the mixing of IMP, the use of the nebuliser device and will also ask about any AEs, including any CCI [REDACTED] due to CCI [REDACTED], and any medical device malfunctions and/or incidents (see [Section 16.3.2](#)).

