18.2. STUDY VARIABLES

Primary Efficacy Variable: The primary variable for this trial is the mean annual NCFB pulmonary exacerbation rate.

Secondary Efficacy Variables

- CCI [REDACTED]

Safety Variables

- incidence of TEAEs;
- absolute changes in percent-predicted FEV₁ from baseline (Visit 2) to end of treatment (Visit 7);
- number of subjects experiencing bronchospasm clinically or spirometrically determined following IMP administration at the start and end of treatment;
- CCI [REDACTED] from Screening/Randomisation (Visit 1/Visit 2) to Visits 3, 5 and end of treatment (Visit 7) as well as on CCI [REDACTED] from Exacerbation Visits and clinic visits due to pneumonia;
- emergence of other bacterial colonies and any developing resistance in CCI [REDACTED] from Screening (Visit 1) to End of Treatment (Visit 7);
- haematology, clinical chemistry and renal function tests;
- physical examination and vital signs data;
- 12-lead electrocardiogram.

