18.4.3. SAFETY DATA

All safety endpoints will be summarised and analysed using the Safety Population.

Incidence of Treatment Emergent Adverse Events

The number and the percentage of subjects reporting TEAEs, treatment emergent SAEs, severe TEAEs, TEAEs leading to discontinuation and TEAEs leading to death will be presented by treatment group, along with the number of events occurring.

TEAEs will also be summarised by System Organ Class and Preferred Term according to MedDRA; they will additionally be summarised by severity and relationship to treatment. A separate summary table will be provided for SAEs.

Only TEAEs, i.e. events with an onset date on or after the date of IMP start, will be included in the summary tables. Individual data listings will include all AEs recorded; a separate listing will be provided for treatment-emergent SAEs.

Number of Subjects experiencing Bronchospasm Clinically or Spirometrically Determined following IMP Administration

The number of subjects experiencing bronchospasm spirometrically determined (a >15% decrease in FEV₁ - not due to poor technique - from pre-bronchodilator baseline in the 30 minutes post-IMP), or clinically determined, will be summarised by treatment. Percentages of subjects in each treatment group and the relative risk for colistimethate sodium group/placebo group will be provided with 95% CI. Treatment differences will be assessed using a Fisher Exact test.

The number and the percentage of subjects experiencing a bronchospasm following IMP administration as clinically determined will also be reported by clinical visit.

In addition, the results for FEV₁ and FVC at each visit will be summarised by treatment. Descriptive statistics for absolute and percentage changes from baseline, i.e. Visit 2 (pre-dose measurement) will be reported.

CCI

The number and percentage of subjects whose CCI at the end of treatment (at 12 months [Visit 7]) will be presented by treatment, overall and by status of previous usage of colistimethate sodium/colistin.

Vital Signs

Descriptive statistics for vital signs at Visit 1 and Visit 7 will be presented overall and by treatment.

Physical examination data

Descriptive statistics for physical examination data at Visit 1 and Visit 7 will be presented overall and by treatment.

Haematology, clinical chemistry and renal function tests

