5.3.4 Section 14.3: Safety

Table 14.3.1.1	Summary of Treatment Emergent Adverse Events	(Safety Population)
Table 14.3.1.2.1	Treatment Emergent Adverse Events by System Organ Class and Preferred Term	(Safety Population)
Table 14.3.1.2.2	Serious Treatment Emergent Adverse Events by System Organ Class and Preferred Term	(Safety Population)
Table 14.3.1.2.3	Related Treatment Emergent Adverse Events by System Organ Class and Preferred Term	(Safety Population)
Table 14.3.1.2.4	Serious Related Treatment Emergent Adverse Events by System Organ Class and Preferred Term	(Safety Population)
Table 14.3.1.2.5	Treatment Emergent Adverse Events Leading to Permanent IMP Discontinuation by System Organ Class and Preferred Term	(Safety Population)
Table 14.3.1.2.6	Fatal Treatment Emergent Adverse Events by System Organ Class and Preferred Term	(Safety Population)
Table 14.3.1.3.1	Treatment Emergent Adverse Events by System Organ Class, Preferred Term and Maximum Severity	(Safety Population)
Table 14.3.1.3.2	Related Treatment Emergent Adverse Events by System Organ Class, Preferred Term and Maximum Severity	(Safety Population)

CONFIDENTIAL

Sponsor:	Zambon S.p.A.	Protocol Number:	Z7224L01
----------	---------------	------------------	----------

Table 14.3.1.4	Most Frequent Treatment Emergent Adverse Events by Preferred Term ($\geq 5\%$ of Subjects with Events in Any Group)	(Safety Population)
Table 14.3.2.1	Listing of Adverse Events Leading to Death	
Table 14.3.2.2	Listing of Serious Adverse Events	
Table 14.3.2.3	Listing of Adverse Events Leading to Discontinuation of Study Treatment	
Please Note: Section 14.3.3 (Narratives of Deaths, Other Serious and Certain Other Significant Adverse Events) is not to be used for any tables		
Table 14.3.4.1.1	Spirometry: FEV ₁ and FVC Results and Change Versus Baseline	(Safety Population)
Table 14.3.4.1.2	Spirometry: Bronchospasm following IMP Administration at Visit 7 (End of Treatment)	(Safety Population)
Table 14.3.4.2.1	Vital Signs: Results and Change Versus Baseline	(Safety Population)
Table 14.3.4.2.2	Vital Signs: Normal/Abnormal NCS/Abnormal CS Results	(Safety Population)
Table 14.3.4.2.3	Vital Signs: Shift Table	(Safety Population)
Table 14.3.4.3.1	Physical Examination: Results	(Safety Population)
Table 14.3.4.3.2	Physical Examination: Shift Table	(Safety Population)
Table 14.3.4.4.1	12-lead ECG: Results	(Safety Population)
Table 14.3.4.4.2	12-lead ECG: Shift Table	(Safety Population)

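### The SAP compares bronchospasm between arms at Visit 7 only, so first-dose cases cannot enter the comparison the protocol planned, and the narrowing is not declared

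*SAP*

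**What the plan says.** **Protocol.** The Summary lists the safety variable as the "number of subjects experiencing bronchospasm clinically or spirometrically determined following IMP administration", with no visit limit. Section 18.2 gives the same variable but ties it to bronchospasm "following IMP administration at the start and end of treatment". Section 18.4.3 defines a case as a fall in FEV1 of more than 15% from the pre-bronchodilator value after IMP, or a clinical determination. It then plans the comparison: "Percentages of subjects in each treatment group and the relative risk for colistimethate sodium group/placebo group will be provided with 95% CI", followed by a Fisher exact test. No visit is named. A separate sentence adds: "The number and the percentage of subjects experiencing a bronchospasm following IMP administration as clinically determined will also be reported by clinical visit".

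**SAP.** Section 2.3 repeats the endpoint with no visit limit. Section 4.8.2 gives numbers, percentages and exact confidence intervals by treatment for Visit 7. For the other visits it says: "The number of subjects experiencing bronchospasm at all other visits will be listed". The relative risk and the Fisher test come next, with the rule "Subjects with no available result will be excluded from the analysis". The only bronchospasm table in section 5.3.4 is Table 14.3.4.1.2, titled "Bronchospasm following IMP Administration at Visit 7 (End of Treatment". Section 4.13 lists the changes from the protocol, does not mention bronchospasm, and states that nothing else changed.

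**The concern.** Protocol section 3.1 describes two periods of airway risk: the first administration, and hyperreactivity that may appear with continued use. A Visit 7 comparison addresses the second. It cannot address the first, because of what happens after a reaction at Visit 2. In the event of a fall in FEV1 above the threshold, "or clinically determined bronchospasm, the subject will be immediately withdrawn from the trial"; sections 11.2 and 14 say the same. A subject who reacts to the first dose therefore has no on-treatment Visit 7 at which that reaction could be counted.

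What is at stake is the one analysis in which bronchospasm, on the protocol's own definition, is compared between arms. As the SAP has it, that analysis describes only subjects who tolerated the drug well enough to be tested a year later. Because the narrowing is not declared, a reader who takes section 4.13 at its word will assume that the protocol's analysis was carried out.

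**Working it through.** The documents give no expected rate, power or sample size for bronchospasm, so there is no figure to reproduce. The check is a comparison of texts, followed by tracing where a first-dose case goes.

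**Step 1. Scope of the variable and of the analysis**

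| Item | Protocol | SAP |
|---|---|---|
| Visits in the variable | Summary: no limit. 18.2: start and end of treatment | 2.3: no limit |
| By-arm percentages | 18.4.3: no visit limit | 4.8.2: Visit 7 |
| Relative risk and Fisher test | 18.4.3: no visit limit | 4.8.2: no visit named, directly after the Visit 7 summary; sole table titled Visit 7 |
| Clinically determined cases by visit | 18.4.3: number and percentage | Not planned; other visits listed |
| Declared as a change | – | 4.13: no |

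The Visit 7 limit on the relative risk and test is an inference. It rests on the order of the paragraphs in SAP 4.8.2 and on the single table title. No other planned output could hold a test at another visit.

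**Step 2. Can a first-dose case enter the numerator?** The flow charts in both documents mark paired pre-bronchodilator and post-IMP spirometry at Visits 2 and 7. A case at Visit 2 is recorded there, and the subject is then withdrawn. SAP 4.1.10 allocates early-termination visits to Visit 7 in the analysis datasets. SAP 4.1.11 says early-termination assessments are listed only, unless stated otherwise. Whichever rule prevails, neither moves a Visit 2 post-dose reading into Visit 7. The answer is no.

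**Step 3. Does the same subject stay in the denominator?** The Safety Population includes anyone who received a dose or part of one, so a first-dose case belongs to it. Under SAP 4.8.2, subjects with no result are excluded. A withdrawn subject would ordinarily have no Visit 7 post-dose result and so would leave the denominator too. This step is less firm than Step 2, because SAP 4.1.10 and 4.1.11 have not been reconciled for early-termination spirometry.

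**Step 4. Is it repaired later?** The SAP addendum limits all its outputs to the mITT population and plans efficacy tables and figures. The later note to file concerns country grouping, the imputation analyses and the tipping-point analysis of the primary endpoint. Neither adds a bronchospasm output.

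**Step 5. Are the data there?** Yes. Visit 2 spirometry before bronchodilator and after IMP is scheduled, and SAP 4.8.2 says the clinical determination is collected on the spirometry forms. Whether paired readings exist at Visits 3 to 6 is unclear: protocol 9.1.6 says only that measurement at other visits follows the same description.

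**The case against.** The strongest reply is that little is lost. Protocol section 14 and SAP section 3.6 treat first-dose bronchospasm as withdrawal due to an adverse event. Such cases should therefore appear by arm in the treatment-emergent event tables, in the table of events leading to permanent discontinuation (SAP 4.8.1.1) and in the reasons for withdrawal (SAP 4.3). SAP 4.8.2 also summarises the pre- to post-IMP change in FEV1 by visit and treatment, and spirometry is listed. Table 14.3.4.1.2 names its visit in its title, so a careful reader is not deceived about what it covers.

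Most of this stands, and it defeats one inference a reader might draw: that first-dose bronchospasm disappears from the report. It does not. But the event tables are organised by coded term and the FEV1 summary describes a distribution. None of them applies the protocol's case definition or yields its percentage, relative risk or test. A clear table title also does not replace a declared change.

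A second reply is that the protocol is not settled on scope: the Summary covers any episode, while section 18.2 names the start and end of treatment. That is fair, and it bars the inference that a pooled start-or-end endpoint is the protocol's comparison, because no passage defines one. It does not rescue the SAP, since no current protocol wording limits the variable to the end of treatment.

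A third reply is that SAP section 4.11 keeps missing subjects in denominators. That rule applies only where nothing else is stated, and section 4.8.2 states otherwise for this table.

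**Conclusion.** The point holds. The SAP narrows a protocol-planned safety comparison to Visit 7, drops the by-visit percentages of clinically determined cases, and declares neither change. First-dose cases cannot enter the numerator of the only planned comparison. Their ordinary absence from the denominator depends on how the early-termination rules are applied.

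No magnitude is claimed, and two tempting figures should not be used.

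- The approximate 10% in protocol section 3.1 covers cough and bronchospasm together and has no split by arm.
- Dropout figures do not count first-dose cases. Planned non-completion of (420 − 340)/420 = 80/420 = 19.0% is from all causes. The SAP 3.9 step from 145 to 188 per arm allows for reduced exposure, so it is not a head count of untested subjects. The 377 recruited is the randomised number, not the number dosed.

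Nor do the documents show which arm the omission would favour. A reader might infer that it flatters the active arm, but that would need a first-dose rate in each arm, which is not given.

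This should be fixed: it affects the reporting of a named safety variable, and the data needed are already collected.

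**What to change.** By addendum, labelled post hoc because the study is unblinded, add one Safety Population table of bronchospasm following IMP, on the definition in protocol section 18.4.3:

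- by treatment: number of cases over number tested, percentage, relative risk with 95% CI and Fisher exact test;
- separate rows for Visit 2 and Visit 7, plus an overall row. State its scope (start or end of treatment, or any visit) after reconciling the protocol Summary, protocol 18.2 and 18.4.3, and SAP 2.3. The protocol specifies no separate Visit 2 test, so label any such test supplementary;
- the number in each arm with no Visit 7 post-dose result.

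Add the number and percentage of clinically determined cases by clinic visit. State how SAP 4.1.10 and 4.1.11 apply to early-termination spirometry. Record the Visit 7 restriction and the dropped by-visit reporting as departures from the protocol.

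The cost is one supplementary table, the by-visit summary and a deviation entry, with no new data collection. The limit is that pre-specification cannot be recovered after unblinding, so the results stay post hoc.

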4.8.3 CCI [REDACTED] to Colistimethate Sodium

The number and percentage of subjects whose CCI [REDACTED] (i.e. CCI [REDACTED]), as per data received from Eurofins central laboratory) CCI [REDACTED] at the end of treatment (at 12 months [Visit 7]) will be presented overall and by treatment. Results will be presented along with number and percentage of subjects with result to susceptibility testing equal to CCI [REDACTED], “Moderate” and “NA”.

The summary will be repeated by status of previous usage of colistimethate sodium/colistin as detailed in [Section 4.1.5](#).

Missing data will not be imputed. A separate summary will be presented summarising the last available results for each subject.

Notes:

- Based on data collected on the Non-CF Bronchiectasis History eCRF form regarding previous usage of colistimethate sodium/colistin, subjects will be classified into:
 - Without any previous usage of colistimethate sodium/colistin;
 - With previous usage of colistimethate sodium/colistin;
 - With missing data regarding previous usage of colistimethate sodium/colistin.

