Section 11.2: Investigational Medicinal Product Dispensing and Administration	A statement has been added to allow patients to continue in the study without pre-bronchodilator use prior to IMP administration.	As stated above, this requirement has been removed due to feedback that, as many patients can tolerate the IMP without it, then the mandated use or a short-acting inhaled bronchodilator prior to IMP administration is an unnecessary burden on patients who would prefer not to use it. The use of the bronchodilator is to aid tolerability not to improve efficacy.
	The timing for the administration of any pre-bronchodilator (at least 10 minutes prior to IMP administration) and post-IMP administration spirometry assessment (30 ± 10 minutes) have been amended.	The timings have been amended to reflect a more practical timeline and to indicate acceptable assessment ranges.
Section 17.8.1: Reporting Serious Adverse Events	The contact details for SAE reporting have been amended.	Contact details have been amended to those relating to the new CRO managing the study.
Section 18.2: Study Variables	Testing for CCI [REDACTED] [REDACTED] has been extended to all clinic visits at which CCI [REDACTED] samples are collected.	As some subjects may be considered eligible for the study based on local laboratory results for the presence of CCI [REDACTED], additional central analyses at Visit 2 may capture some additional pre-existing resistance data. At Visit 3 we will also look at the CCI [REDACTED]. This is to identify if a pre-existing resistant strain present before commencement of IMP is growing preferentially if the IMP is suppressing the growth of susceptible strains. This will help differentiate from emergent resistance that may develop throughout the course of the study.
Section 26: References	The date for the reference UK SmPC for Promixin has been amended from 2018 to 2019.	Annual update to the SmPC.
	The date the relevant web-site for the CCI [REDACTED] reference was last known/accessed has been included.	The web-site no longer appears to be operational.

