2.3 Safety Endpoints

The safety endpoints of this trial are:

- incidence of treatment emergent adverse events (TEAEs);
- absolute changes in percent-predicted forced expiratory volume in 1 second (FEV₁) from baseline to each post-baseline visit;
- the number of subjects experiencing bronchospasm clinically or spirometrically determined following IMP administration;
- CCI [REDACTED] from Screening/Randomisation (Visit 1/Visit 2) to Visits 3, 5 and end of treatment (Visit 7) as well as on sputum from Exacerbation Visits and clinic visits due to pneumonia;
- CCI [REDACTED] from Screening (Visit 1) to End of Treatment (Visit 7);
- haematology, clinical chemistry and renal function tests;
- physical examination and vital signs data;
- 12-lead electrocardiogram.

CONFIDENTIAL

Sponsor:	Zambon S.p.A.	Protocol Number:	Z7224L01
----------	---------------	------------------	----------

3 Study Design

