Table 14.3.4.5.1.1	Haematology: Results and Change Versus Baseline	(Safety Population)
Table 14.3.4.5.1.2	Haematology: Shift Table	(Safety Population)
Table 14.3.4.5.2.1	Clinical Chemistry: Results and Change Versus Baseline	(Safety Population)
Table 14.3.4.5.2.2	Clinical Chemistry: Shift Table	(Safety Population)
Table 14.3.4.6.1	CC [REDACTED] at Visit 7 (Overall and by Previous Use of Colistimethate Sodium/Colistin)	(Safety Population)
Table 14.3.4.6.2	CC [REDACTED] (Last Available Data) (Overall and by Previous Use of Colistimethate Sodium/Colistin)	(Safety Population)

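### The planned colistimethate susceptibility tables cover only Visit 7 and the last available result, so on the visible text they do not identify resistance that emerged within a subject

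*SAP*

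**What the plan says.** SAP 2.3 lists a safety endpoint whose noun is redacted but whose span is visible: "from Screening/Randomisation (Visit 1/Visit 2) to Visits 3, 5 and end of treatment (Visit 7) as well as on sputum from Exacerbation Visits", and also samples from clinic visits for pneumonia. Protocol 18.2 has the same span and adds a second variable, "emergence of other bacterial colonies and any developing resistance", from Visit 1 to Visit 7.

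The Summary of Key Changes for protocol version 7.0 (entry for Section 18.2) explains why testing was extended to every visit with a sample. Visit 2 may pick up resistance already present, and Visit 3 may show whether a pre-existing resistant strain is growing preferentially under treatment. It concludes: "This will help differentiate from emergent resistance that may develop throughout the course of the study".

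For the analysis, SAP 4.8.3 gives subjects "at the end of treatment (at 12 months [Visit 7]) will be presented overall and by treatment", shown along with the "number and percentage of subjects with result to susceptibility testing equal to" a redacted category, Moderate and NA. The summary is repeated by previous colistimethate/colistin use. Missing data are not imputed. It then says: "A separate summary will be presented summarising the last available results for each subject". The index in SAP 5.3.4 has two matching tables: 14.3.4.6.1, "at Visit 7 (Overall and by Previous Use of Colistimethate Sodium/Colistin", and 14.3.4.6.2, on last available data with the same split.

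**The concern.** The endpoint and the reason given for the extra testing both concern what happens between baseline and later visits. The visible analysis is a status count at one visit and at one last sample. A subject resistant before the first dose and still resistant at Visit 7 is counted in the same cell as one who became resistant on treatment. Previous colistin use is the only stratifier, and it is a history item rather than a baseline susceptibility result.

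At stake is what the trial can say about emergent resistance over 12 months of an inhaled antibiotic. Protocol Section 3 reports that the sponsor's earlier trial, of up to 6 months, gave no evidence that treatment led to colistin-resistant isolates. The planned tables would not support a statement of that kind here without going back to the listings.

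**Working it through.** The plan states no figure to reproduce, so the check sets sections side by side and then asks what the planned tables can identify.

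**1. Collected and tabulated**

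| Sample | In the endpoint (SAP 2.3) | Visible susceptibility table |
|---|---|---|
| Visit 1/2 (baseline) | yes | none |
| Visit 3 | yes | none |
| Visit 5 | yes | none |
| Visit 7 | yes | 14.3.4.6.1 |
| Exacerbation or pneumonia visit | yes | none |
| Last result per subject | not named | 14.3.4.6.2 |

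Table 14.1.9 gives presence of *P. aeruginosa* at Visit 1, not its susceptibility. SAP 4.1.6 defines a sputum baseline (Visit 2 before the first dose, otherwise the last earlier value), but the visible text of 4.8.3 does not use it. SAP 4.8.4 to 4.8.7 give shift tables from baseline, including the most extreme or worst later result, for laboratory data, vital signs, physical examination and ECG. SAP 4.13 lists no change for susceptibility.

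**2. How four possible histories are counted** (S = susceptible, R = resistant)

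| History | Visit 7 table | Last available | Emergent? |
|---|---|---|---|
| R at Visit 2, R at Visit 7 | R | R | no |
| S at Visit 2, R at Visit 3, S at Visit 7 | S | S | yes |
| S at Visit 2, R at Visit 5, then withdrawn | no result | R | yes |
| R at Visit 2, withdrawn after the first dose | no result | R | no |

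The fourth history can occur. Protocol 8.2 withdraws a subject at once for bronchospasm after the first dose, and that subject is in the Safety Population with pre-dose sputum results only.

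**3. What one margin identifies.** Let p0 be the proportion resistant at baseline, p7 the proportion resistant at Visit 7, and e the proportion who were not resistant at baseline and are resistant at Visit 7. Then

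max(0, p7 − p0) ≤ e ≤ min(p7, 1 − p0).

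The documents give no rates, so these values are assumptions.
- p7 = 10%, p0 not tabulated: e lies between 0% and 10%.
- p7 = 10%, p0 = 8%: lower bound 0.10 − 0.08 = 2%; upper bound min(0.10, 0.92) = 10%.

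A baseline column alone would therefore still leave 2% to 10%. Only a cross-tabulation within subjects fixes e.

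**4. What randomisation preserves.** Assume 4% resistant at baseline in each arm, 3% newly resistant on active and 0% on placebo, with no resistance lost. Visit 7 then shows 4% + 3% = 7% against 4%. The difference, 7% − 4% = 3 points, equals the assumed emergent effect. The ratio 0.07/0.04 = 1.75 does not describe new resistance, which is 0.03/0.96 = 3.1% against 0% among subjects not resistant at baseline.

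**The case against.** **Redaction.** The predicate of the main sentence in SAP 4.8.3 is blacked out, as it is in its parent, protocol 18.4.3. A phrase meaning that subjects became resistant cannot be excluded. This stands as a caveat: the absence of a baseline is inferred from the visible result categories and the two table titles. The lack of tables for Visits 3 and 5 and for exacerbation samples does not depend on redacted words.

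**The endpoint may be a testing schedule.** The visible wording can be read as saying when samples are tested, and the reason for extending testing does not promise a shift table. That is fair. SAP 4.8.3 follows protocol 18.4.3 and adds a table to it. The stated purpose of the extra samples is still not served by any visible table.

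**Randomisation.** Baseline resistance is balanced in expectation, so the Visit 7 difference is informative. This stands. A reader might infer that the trial can say nothing about emergent resistance. Step 4 of the working shows that this goes too far.

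**Withdrawn subjects and denominators.** A reader might infer that resistance is lost whenever a subject leaves early. The last-available table does capture a final resistant result. A reader might also infer that the percentages rest only on subjects who still grow the organism. The documents do not support this: SAP 4.1.3 and 4.11 put all subjects, including those with missing values, in the denominator by default. SAP 4.8.3 has an NA category, and SAP 4.8.2 says so expressly where subjects without a result are dropped.

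**Other routes.** Protocol 9.1.6 keeps Visit 1 and Visit 7 isolates for later analysis and makes a greater than four-fold MIC change a trigger for optional genotyping. Protocol 8.6 recalls subjects resistant at Visit 7. Listing 16.2.8.7 holds sputum results by subject. Emergence could thus be worked out afterwards, but a listing is not a by-arm summary.

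**Conclusion.** The point holds as a gap in descriptive safety reporting that is cheap to close. On the visible text, the planned tables do not identify emergence within subjects, do not use the baseline the SAP itself defines, and miss resistance at Visit 3, Visit 5 or an exacerbation that is absent from the last sample. The last-available summary as worded can also count a pre-dose result as the outcome.

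The size cannot be stated from the documents, because they contain no resistance rates; the ranges above rest on assumed values. The conclusion assumes that the redacted words in SAP 4.8.3 do not already describe a comparison within subjects. It does not mean that the Visit 7 comparison between arms is uninformative, and it has no bearing on alpha, power or the primary endpoint.

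**What to change.** In SAP 4.8.3:
- Add by-arm shift tables from baseline (as defined in 4.1.6) to Visits 3, 5 and 7 and to the worst post-baseline result, including exacerbation samples. Keep NA/no isolate as its own category and use the SAP's default denominator.
- Report by arm the number and percentage newly resistant among subjects not resistant at baseline.
- Restrict the last-available summary to results after the first dose.
- Optionally, add by-arm counts of subjects with a greater than four-fold MIC rise and of newly isolated other species.

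The SAP Addendum (2.2) states that the database is locked and the study unblinded, so tables added now should be labelled post hoc, as SAP Section 1 requires. The cost is a few descriptive tables from existing central laboratory data.
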